To accomplish these goals, our outpatient clinic is open Monday thru Friday offering 4 different appointment times. All patients that are referred to our clinic for TAP, first receive a vein evaluation to see if the patient is a candidate for peripheral IV therapy. At our clinic, approximately 68% of our TAP's are performed peripherally. This eliminates the risk of a central line infection and any alteration in activities of daily living, such as bathing(Kramer, 2016), (Shang, Ma, Poghosyan, Dowding, & Stone, 2014),(Keller et al., 2018; McDiarmid, 2015).

Our hypothesis, is that the 20-gauge BD Nexiva Diffusics catheter provides the same efficacy as current practice with no increase in adverse events for patients undergoing therapeutic apheresis. The results from our study will be significant because if the 20 guage needle is equally effective for TAP, it can increase the number of patients that would be candidates for peripheral therapy. Therefore, decreasing the need for central venous access, which place the patient at an increased risk of infection. Our study is a comparison of 2 types of infusion catheters. The standard of care is an 18-gauge autogard catheter (control group) which will be compared to the 20-gauge BD Nexiva Diffusics (intervention).

- P patients who require therapeutic apheresis procedures (TAP)
- I use of 20G BD diffusics catheter during apheresis
- C use of 18 G standard of care IV catheter during apheresis
- O no difference in efficacy and no increase in safety events

Concise Summary of Project

This is a randomized pilot study of TAP using the current standard of care catheter (SOC) vs the BD Nexiva Diffusics Catheter. It is a single blinded, randomized study. Data will be used to refine and power a full randomized control trial. For this study, a sample of 33 encounters in each group (total of 66 encounters). Our specific aim is to test the hypothesis that the 20-gauge BD Nexiva Diffusics Catheter provides the same efficacy and lower pain level with no increase in adverse events for patients undergoing apheresis treatments.

Randomization Procedure

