After an eligible participant is consented to the study the patient will be randomized without replacement to the use of one of the two catheters. Using a random number generator, numbers between (1-66) were randomly divided into two groups: SOC Control group and BD Intervention group (Figure 1). A study identification number (SID) key will be saved on a UTSW approved secure device and only the research coordinator will have access to the SID key showing which SID coordinates with each group. This will ensure that unblinding can occur is necessary and there is a backup to randomization.

The research coordinator will have 66 randomized envelops without replacement. Half of the envelops will be assigned to 18G catheter SOC (control) and the other half be assigned to

20G BD Nexiva Diffusics catheter (intervention). The PI will be blinded, therefore the PI will pick an envelope when patients are consented and ready for treatment. Participants will be randomized after they have consented to the study. Participants' will then be randomized to one of the two groups again at each encounter (i.e., SOC visit). Inside the envelope it will tell the investigator if the patient is in the control or intervention group of the study.

To promote a more representative sample, each patient may participate a maximum of 10 times.

Study procedure:

[figure not shown]
Each enrolled patient will participate in the study will be randomized at each encounter. During each encounter the following information will be captured:

- 1. CBC
- 2. Patient discomfort

level with placement of catheter

- 3. Inlet rate
- 4. Return line pressures
- 5. Procedures alarms
- 6. Procedure total time
- 7. Post procedure sample

Treating nurse (RN) will start the TAPs procedure with one of the 2 catheters. During the intervention period, the RN will be at bedside during as it is SOC in the Apheresis unit however for the purpose of this study the RN will have the study data collection form (DCF, Appendix1). The RN will complete the pre-assessment including a pain assessment to establish pain level prior to procedure that is currently documented in the electronic medical record. The patient will be asked to self-report the pain level after the return line has been started on the visual analog scale (VAS) Scale from 0mm to 100mm "0 being the lowest/ no pain, 100mm being the highest

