level of pain". The VAS scale will be used for both the SOC and intervention group to compare the pain level when starting the return line. The RN will collect a CBC before the start of the procedure which will be used in the programing of the TAP procedure. The RN will start recording the "inlet rate, return line pressures, and alarms" every 15 minutes until the procedure is completed.

Before patient disconnects, and after the completion of procedure sing the same therapeutic apheresis procedure access site, a blood sample will be drawn by the RN 2 lavender top tubes (4ml) for plasma hemoglobin test. The plasma hemoglobin test will be sent to the UTSW lab for analysis of hemoloysis and results will be sent back directly to the PI. Blood sample results will be collected by the PI or the study team in an excel spreadsheet (CRF) that will be saved on a secure drive on the UTSW campus.

Hemolysis is defined as the destruction of red blood cells which leads to the release of hemoglobin from the red blood cells into the blood plasma. Each patient will be tested for hemolysis by running plasma hemoglobin test after the procedure has finished. This will be collected in a two lavender tops (4ml) The cost for this test is covered by sponsor and because the patient has an indwelling access to venous blood there will no charge for drawing the sample.. There is no clinical suspicion that the use of the 20-gauge BD Nexiva Diffusics Catheter will increase this risk. Hemolysis will be scored dichotomously as present or absent for each encounter.

Pain is defined as any increase discomfort experienced by the patient associated with the apheresis procedure. The current standard of care is to ask the patient "are you having pain" and then ask them to rate the pain from 0 to 10. For this study, one additional question will be asked after the patient's vein has been accessed (IV catheter in place). The patient will self-report their pain using a 100 mm VAS scale. "*The VAS has been used by healthcare providers to measure the characteristics of disease severity in each patient individually*"(Klimek et al., 2017) Currently, all peripheral apheresis patients have some pain/discomfort while having a treatment, however; it is usually tolerated with minimal complaints.

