Measures of Quality of Apheresis will include inlet rate, and return pressures, procedure time. These measures are all readily available in the electronic medical record (EMR) and are all currently recorded as standard of care. The inlet rate is defined as the percent of patient inlet rate divided by the maximum allowable inlet rate. Because inlet rates are different for each type of TAP has a different maximum inlet rate, this will allow standardization across procedures. The max inlet rate for Photopheresis is 50ml/sec, the max inlet for plasma exchange is 100ml/sec inlet for red blood cell exchange is 55ml/sec. In addition, the inlet rate for each participant in the intervention arm will be compared to the average of their last 5 procedures. This measure will compare the efficiency of the SOC verses the intervention.

Inclusion Criteria

- Adult (≥ 18 years old)
- Speaks and reads English
- A patient of the Apheresis clinic at UT Southwestern University Hospital and Clinics
- Scheduled to receive TAP (therapeutic plasma exchange, red blood cell exchange and extracorporeal Photopheresis) as standard of care

Exclusion Criteria

- Prisoners
- Persons under the age of 18 years
- Patient who are actively involved in chemotherapy

Sources of Research Material

There are three sources of data for this study: electronic medical record (EMR) and paper-and-pen data collection from the patient's bedside (Data Collection form), and lab results provided by the UTSW laboratory via EMR. The EMR data that will be collected will include demographic information such as: age, sex, race, ethnicity, and admission diagnosis. The paper-and pen-data collection will include the patient self-reported pain level (VAS Scale), CBC collection, procedure data (minutes, inlet rate, return line pressures and alarms) total procedure time and post procedure sample. The paper-and-pen data collection form (Appendix 1) will record data only during patients TAP's encounter. Blood sample will be obtained from a SOC line. An additional 8 ml's for blood will be drawn from the patients for research purposes. Results from the bloodwork will be provided by the UTSW laboratory via the patient's EMR.

Recruitment Methods and Consenting Process

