be replaced with the SOC 18-gauge catheter. Obtaining blood samples may cause some discomfort, feeling lightheaded, fainting, bruising, clotting, and bleeding from the site of the needle stick and, in rare cases, infection. The risks are mitigated by drawing blood from a line that has already been established as part of SOC.

There is a low risk of breach in confidentiality. Subjects will be assigned individual study identification (SID) numbers and no personal identifiers will be included in the final summary.

Patients who are randomized to the 20-guage needle group and who fail the intervention will be given the 18-guage standard of care needle. At the patient's next visit, the patient will once again be randomized. If the patient is randomized into the 20-guage needle arm and fails the intervention a second time, the patient will be removed from the study.

Procedures to Maintain Confidentiality

Study participants will be given a study identification (SID) number. Only the approved study personnel and the principal investigator have access to the database linking the SID to the patient name. This database is kept on a protected drive on a password protected computer. Paper or hard copy participant records will be kept in a locked file cabinet in a locked office. If any identifying information is transmitted, it will be done so via secure e-mail and/or dedicated fax machines.

Statistical Analysis Plan

All data will be first collected on the DCF (Appendix I) and then entered into an electronic spreadsheet (e.g., MS Excel) which will be converted to SAS v 9.4 for analysis. All statistical analyses will be performed at UTSW in a location with secure data encryption capability. Initially, the data will be summarized first using standard measures of central tendency (mean, median, standard deviation, and interquartile range) for each variable. These will be examined to support the assumption of being approximately normally distributed. Baseline characteristics will be summarized using appropriate parametric and non-parametric measures.

The primary hypothesis is that the 20-gauge BD Nexiva Diffusics catheter provides the same efficacy of current practice with no increase in adverse events for patients undergoing therapeutic apheresis. This will be examined in 2 steps. First, ANOVA will be used to explore

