efficacy wherein efficacy is represented by 1) the plasma hemoglobin value, and 2) the amount of time (minutes) required to complete a TAP. Hence models will be constructed to compare the mean plasma hemoglobin values by group, and to compare the mean number of minutes to complete TAP by group. Second, ANOVA will be used to compare the mean number of adverse events subjects experience in each group (intervention vs control).

Finally, a planned secondary analysis is to examine if the percent of lumen occupied by the return catheter is associated with return pressures. The suggested standard is that a catheter occupies < 45% of the inner-lumen diameter (measured with ultrasound). Return pressures >400 mm Hg are considered problematic. Chi-square analysis will be used to explore the odds of experiencing a return pressure > 400 mm Hg when the return catheter occupies <45% of the inner-lumen diameter.

Item	Month 1-2	Month 3-6	Month 4-8	Month 9-11	Month 12-18
IRB approval	Х				
Consent/	Х	X			
Enrollment					
Randomization	Х	X	Х	Х	
Data collection	Х	Х	Х	Х	
Manuscript				Х	X
prep					
Study closeout					X

Project Timeline

Enrollment of first patient (month 1), enrollment of the last patient (month 12), completion of data analysis (month 14), and manuscript submission (month 18). The apheresis team see approximatley 3000 TAP treaments each year. Of these, approximately 1500 encounters will meet the primary inclusion criteria. We anticipate that it will take less than 1-year to complete the study.

Future directions

The intention of this pilot study is to test the 20-gauge BD Nexiva Diffusics Catheter performance and efficacy. The findings from this study will be used to provide additional preliminary data to BD to support a National Institutes of Health or Agency for Healthcare Research and Quality (AHRQ) application (pending 2017 AHRQ funding announcements). Stakeholder feedback will be provided through an optional de-identified report to all patients and families.

Presentation of data

It is anticipated that the results from this study will be presented to American Society for Apheresis at their annual convention. The results will also be summarized in a manuscript and submitted for peer-review publication to Journal of Clinical Apheresis.

Appendix 1

Patient Sticker

A Randomized Trial Examining Plasma Exchange using the BD Catheter In an Outpatient Apheresis Unit The "REPLACE" study

Date SID Procedure Type						

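### The minutes comparison makes no use of the pre-procedure CBC taken at every encounter; adjusting for it, after procedure type and patient, could sharpen the estimate at little cost

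*Combined protocol and SAP*

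**What the plan says.** CBC. It is the first item in the Study procedure list introduced by "During each encounter the following information will be captured". The same section gives its timing and use: "The RN will collect a CBC before the start of the procedure which will be used in the programing of the TAP procedure". It is therefore planned for both arms at every visit, before the procedure begins.

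Analysis. Minutes is one of two efficacy measures in the Statistical Analysis Plan. The method is given as "First, ANOVA will be used to explore" efficacy, and the minutes model is built "to compare the mean number of minutes to complete TAP by group". No covariate is named: not the CBC, the procedure type or the patient.

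Size and purpose. The Concise Summary of Project plans "a sample of 33 encounters in each group (total of 66 encounters" and describes a pilot: "Data will be used to refine and power a full randomized control trial".

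Data route. The form in Appendix 1 has only a Yes/No tick for CBC collection and no field for a value. Sources of Research Material says: "Results from the bloodwork will be provided by the UTSW laboratory via the patient's EMR".

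**The concern.** A measurement used to program the procedure is a natural candidate for explaining how long the procedure takes, whichever catheter is in place. It is taken before the return catheter has had any chance to perform, so adjusting for it is legitimate. The model as written leaves any such variation in the error term.

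The trial wants to say that the two catheters have the same efficacy, and it has 66 encounters. What it can say about similarity in minutes depends on the width of the interval for the difference. The protocol itself lists a longer procedure as a possible risk of the smaller catheter. Avoidable noise makes a real delay harder to see, and a non-significant ANOVA could then be misread as sameness.

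The pilot is also meant to supply planning figures for a larger trial. The residual SD of minutes and its relation to the CBC are such figures, and the planned analysis would not report that relation.

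**Working it through.** **1. The plan's own figure.** The plan gives 33 per group without alpha, power, SD, effect size or margin, so it cannot be reproduced. Back-solving is not unique. A difference of 0.69 to 0.70 SD (two-sided 0.05, 80% power) gives 33 per group, and so does 0.80 SD at 90% power. So does a non-inferiority margin of 0.70 SD (one-sided 0.025, 80% power).

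**2. Unadjusted precision**, in SD units, treating encounters as independent (an assumption; patients may contribute up to 10):
- SE of the difference = sqrt(2/33) = 0.246 SD
- Detectable difference at two-sided 0.05 and 80% power = (1.960 + 0.842) × 0.246 = 0.69 SD

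**3. Effect of a covariate.** Let R² be the share of the remaining variance in minutes that the CBC value explains, q the number of CBC slopes, and v the residual degrees of freedom before they are added. Approximately:

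width ratio = sqrt(1 − R²) × sqrt(1 + q/(v − q − 1))

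The first factor is the gain and the second is the cost of estimating the slopes. With an intercept, catheter group and three procedure types, v = 66 − 4 = 62. The cost factor is
- one slope: sqrt(1 + 1/60) = 1.008
- three slopes, one per procedure type: sqrt(1 + 3/58) = 1.025

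The documents give no R², so a range is shown:

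| R² (assumed) | sqrt(1 − R²) | Change in width, one slope | Change in width, three slopes |
|---|---|---|---|
| 0% | 1.000 | +0.8% | +2.5% |
| 5% | 0.975 | −1.7% | about 0 |
| 10% | 0.949 | −4.3% | −2.7% |
| 20% | 0.894 | −9.8% | −8.3% |
| 30% | 0.837 | −15.6% | −14.2% |

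Allowing for the slightly larger t-quantile changes these by about 0.1 percentage point or less.

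**4. Break-even.** The ratio equals 1 when R² = q/(v − 1): 1/61 = 1.6% for one slope and 3/61 = 4.9% for three.

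**5. In encounters.** Equivalent number = 66 / (width ratio)². With one slope this is 66/(0.90 × 1.0167) = 72, 66/(0.80 × 1.0167) = 81 and 66/(0.70 × 1.0167) = 93 at R² of 10%, 20% and 30%.

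**6. Sensitivity to the patient term.** The Recruitment section expects 30 participants. If all 30 entered as fixed effects, v would be about 66 − 30 − 1 = 35. One slope then costs sqrt(1 + 1/33) = 1.015, and the narrowing at R² = 10% is 1 − 0.949 × 1.015 = 3.7%. Three slopes cost sqrt(1 + 3/31) = 1.047, and the narrowing at 10% is 1 − 0.949 × 1.047 = 0.6%. A random patient effect should generally use fewer degrees of freedom than this. The single slope is the safer default.

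**The case against.** The strongest objection is that the documents do not show that the CBC affects minutes at all. They say that it is used in programming. They do not say which component is used, which setting it changes, or that duration follows from it. A reader might infer that known variation is being left in the error term, that hematocrit is the driver, and that it shifts from visit to visit within a patient. The text supports none of these: hematocrit is never mentioned, no CBC values are given, and no correlation with minutes is stated. This part of the objection stands. The link is plausible, not demonstrated.

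Second, better-documented sources of variation are missing from the same model. The protocol describes three procedure types with different maximum inlet rates and allows each patient up to 10 encounters. Those should enter first, and a CBC term without them may recover little. This also stands, and the fix reflects it.

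Third, this is an exploratory pilot with no stated power, margin or SD, so no declared target is missed, and an unadjusted comparison is a valid choice. That is correct, but it does not remove the case for a cheap gain in precision, or for a pilot to estimate a relation that the next trial could use.

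Fourth, the gain can vanish. With three slopes it is nil at R² of about 5%. That is a reason to default to one slope rather than to omit the covariate.

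**Conclusion.** The point holds as a modest matter of precision. The minutes model ignores a pre-procedure measurement that is collected at every encounter in both arms and used in programming, and which may explain part of the variation in minutes.

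A reader might go further and infer that the unadjusted comparison is biased. The documents do not support that: the catheter is randomized again at each encounter, so omitting the CBC does not by itself favor either arm.

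With one slope the interval would be about 4%, 10% or 16% narrower if R² were 10%, 20% or 30% of the remaining variance. It would be unchanged at about 2% and at most about 1% wider if the CBC explained nothing; with three slopes the worst case is about 3% wider. These figures rest on assumed R² values, independent encounters and about 62 residual degrees of freedom. Clustering within patient, or fixed patient effects, would change them. The possible loss is small and bounded, while the possible gain is larger but unproven.

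**What to change.** In the Statistical Analysis Plan, pre-specify the minutes model with:
- catheter group;
- procedure type;
- a random effect for patient;
- the pre-procedure CBC value actually used in programming, named by the study team, as a single slope unless there are enough encounters per procedure type for separate slopes.

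Report the adjusted catheter difference with a 95% confidence interval alongside the unadjusted one. Report also the residual SD and the CBC coefficient, as planning inputs for the full trial.

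Add a field for the CBC value to the Appendix 1 form, or a stated EMR extraction step, because the form now records only whether the sample was collected.

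The cost is a few sentences in the plan, identification of the relevant CBC value, and one extracted number per encounter (66 in all). The CBC is already planned at each encounter, so no extra blood draw is needed. Statistically it uses one degree of freedom for a single slope, or three for separate slopes, beyond the procedure-type and patient terms.

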For this study, patients will be recruited from the Apheresis Unit at UT Southwestern University Hospital and Clinics by a member of the research team. A member of the research team will screen the electronic medical record to determine a patient's eligibility. If a patient appears eligible for the study a member of the research team will discuss eligibility criteria with a member of the clinical team (nurse manger, nurse, physician, resident, fellow, social worker). The researcher will communicate with the clinical team to ensure eligibility: adult (≥18 years old), speaks and reads English, admitted to the Apheresis Unit at UT Southwestern University Hospital and Clinics at the time of consent. All patients in this study will be able to provide selfconsent (read and speak English).

When a patient is deemed eligible, a member of the research team will discuss consent and study procedures with that patient, in a place that is comfortable for the patient. After being approached by a member of the research team, patients will have up to next visit to consider participation in the study. The study team expects recruitment of 30 participants to last approximately 8 months. (Table 1)

Potential Benefits

There may or may not be a direct benefit to the participants in this study. Any additional blood test result that seems out of the norm will be shared with the nurse on duty or treating physician. We would also hope to share this with the greater research and clinical community in hopes of finding an alternative way for apheresis patients to have therapeutic apheresis procedures with less pain and no increase in adverse events.

Potential Risks

Risks associated with BD Cather:

Longer procedure time might occur if the inlet rate of the treatment is slower. The patient will be informed of this during the ICF process. With smaller catheters there's a risk of not obtaining the appropriate return rate for the patient. When the return rate is out of the SOC parameters the SOC apheresis equipment (Optia or Cellex) will alarm. If the alarm sounds 3 times the RN will decrease inlet rate by 5 ml/sec until the minimum threshold is reached (if needed), which is 50 ml/sec for plasma exchange and 35 ml/sec for RBC exchange and 20 ml/sec for photopheresis. If the alarm continues to when the minimum threshold is reached the catheter will

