Instructions:	Please complete the following form except for the VAS scale. Must be completed by patient to measure the characteristics of pain severity. Please circle option that apply.					
Collect CBC	Yes	Νο				
Catheter type	18 GA BD Autogard	20 GA BD Nexiva Diffusics				
Vein diameter w/tourniquet:	Vein diameter w/o turniquet:	Vein diameter Procedure Running:				
Asses pain after return placement						
Please rate your current pain by drawing a vertical line across the bar below						

vere		Extremely Severe		
		Procedure d	ata	
tart time:				
Inlet rate	Return line pressures	Alarms	Comments	
	tart time:	tart time: Inlet rate Return line	Procedure da tart time: Inlet rate Return Alarms line	

Total Procedure time:	Procedure en	Procedure end time:		Final Inlet Volume/Blood Processed:	
Collect post proceduer Plasma Hemoglobin	Yes		No		

References

- Golestaneh, L., & Mokrzycki, M. H. (2013). Vascular access in therapeutic apheresis: update 2013. *Journal of clinical apheresis, 28*(1), 64-72.
- Kalantari, K. (2012). The choice of vascular access for therapeutic apheresis. *Journal of clinical apheresis*, 27(3), 153-159.
- Keller, S. C., Williams, D., Rock, C., Deol, S., Trexler, P., & Cosgrove, S. E. (2018). A new frontier: Central line–associated bloodstream infection surveillance in home infusion therapy. *American journal of infection control*, 46(12), 1419-1421.
- Kramer, N. (2016). Monitoring Central Line-Associated Bloodstream Infections (CLABSI) in Home Infusion. *Infusion*, 22(4), 35-44.
- McDiarmid, S. (2015). Reduce the risk of infection by reducing the need for central lines: using ultrasound guidance to establish peripheral access in patients with sickle cell disease undergoing red cell exchange apheresis. *Journal of clinical apheresis*, *30*(2), 98-99.

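### Return pressure is entered every 15 minutes with no rule for peaks, so the secondary analysis of pressures above 400 mm Hg can under-count its event

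*Combined protocol and SAP*

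**What the plan says.** **Recording.** Under Study procedure, inlet rate, return line pressures and alarms are entered "every 15 minutes until the procedure is completed". Sources of Research Material assigns "procedure data (minutes, inlet rate, return line pressures and alarms" to the paper form. The legible columns of the form in Appendix 1 are inlet rate, "Return line pressures", alarms and comments. No section says whether the pressure entry is the value at that moment or the highest since the last row. None requires the pressure at an alarm.

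**A second record.** The paragraph on quality of apheresis says of inlet rate, return pressures and procedure time: "These measures are all readily available in the electronic medical record (EMR) and are all currently recorded as standard of care". It gives no logging frequency. The medical-record items named in Sources of Research Material are demographics and diagnosis.

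**Analysis.** In the Statistical Analysis Plan, "a planned secondary analysis is to examine if the percent of lumen occupied by the return catheter is associated with return pressures". The threshold is stated as "Return pressures >400 mm Hg are considered problematic", and the method as "Chi-square analysis will be used to explore the odds of experiencing a return pressure > 400 mm Hg", by whether the catheter takes up less than 45% of the lumen.

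**Alarms.** Potential Risks says that the equipment alarms when the return rate leaves its standard limits, and then "If the alarm sounds 3 times the RN will decrease inlet rate by 5 ml/sec until the minimum threshold is reached (if needed". No section ties an alarm to 400 mm Hg.

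**The concern.** Whether a pressure above 400 mm Hg was experienced is an ever/never question about the whole procedure. An entry every 15 minutes answers a different one: what the pressure was at a few moments. Nothing requires a rise and fall between two rows to be written down. Barring a misread value, the error runs one way, because a reading can miss an excursion but cannot create one.

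Two things are at stake. The chi-square may have few events to work with. And the Concise Summary says that the pilot's data will inform the design and power of a full trial, so an event rate that is too low would carry forward. If no other log of sufficient frequency exists, unrecorded values cannot be recovered afterwards.

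**Working it through.** **Inputs from the documents:** a 15-minute interval (Study procedure); a 400 mm Hg threshold (Statistical Analysis Plan); 33 encounters per group (Concise Summary).

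**The plan's own figure.** 33 + 33 = 66 encounters, as stated. The plan gives no event rate, detection rate or power for the >400 mm Hg analysis, so nothing further can be reproduced.

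**Assumptions.** Each entry is an instantaneous reading. Excursions start at times unrelated to the reading and are independent of one another. Their durations and number are assumed, because the documents give none.

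**Capture of one excursion of d minutes:** min(1, d/15).
- 1 min: 1/15 = 6.7%
- 2 min: 2/15 = 13.3%
- 5 min: 5/15 = 33.3%
- 7.5 min: 7.5/15 = 50%
- 10 min: 10/15 = 66.7%
- 15 min or more: 100%

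A simulation at 1, 5 and 7.5 minutes gave 6.7%, 33.4% and 50.0%.

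**Capture of at least one of k excursions in an encounter:** 1 − (1 − d/15)^k.
- 1-minute excursions: 6.7% for k = 1; 18.7% for k = 3; 29.2% for k = 5; 49.8% for k = 10
- 5-minute excursions: 33.3% for k = 1; 55.6% for k = 2; 70.4% for k = 3

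**Effect on the chi-square (illustration).** Assume true encounter-level rates of 50% and 20%, and 33 encounters in each lumen-occupancy group. That split is an assumption; the 33 per group in the plan refers to catheter arms. Capture is assumed equal in the two groups, and encounters are treated as independent although a patient may contribute up to 10.
- Full capture: 33 × (0.50 + 0.20) = 23.1 expected events; power 0.735; odds ratio 4.0
- 33.3% capture: 23.1 × 0.333 = 7.7 events; power 0.241; odds ratio 2.8
- 6.7% capture: 23.1 × 0.067 = 1.5 events; power 0.077; odds ratio 2.55

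The risk ratio stays at 2.5 throughout, so under equal capture the main loss is events and precision.

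**The case against.** The strongest reply is that the premise is inferred. The text does not call the entry a spot reading, and an alarm entry most naturally covers everything since the last row, so the pressure entry might too. That is fair, but if a peak is meant, the form and the plan need to say so.

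Second, the paper form is not the only record, since pressures are also in the medical record. This stands as a limit on the point. It does not remove it, because neither the logging frequency nor any use of those values in this analysis is given.

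Third, a reader might infer that most excursions are missed. The documents do not support that. A single excursion is missed more often than not only if it lasts under 7.5 minutes, and repetition helps. Read the slow-down rule as three alarms per step and suppose, without support in the text, that each alarm is a 1-minute excursion above 400 mm Hg. Plasma exchange then has (100 − 50)/5 × 3 = 30 alarms before the floor, and 1 − (14/15)^30 = 87% of such encounters would show at least one value above 400. For photopheresis, (50 − 20)/5 × 3 = 18 alarms give 71%; for red cell exchange, (55 − 35)/5 × 3 = 12 give 56%.

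Fourth, because the slow-down is written under the risks of the BD catheter, a reader might infer that the 20-gauge arm will look falsely free of pressure problems. The planned test is by lumen occupancy, not by arm. Slowed encounters could also show in inlet rate, alarms, procedure time and catheter replacement. Unequal capture by occupancy is possible, but nothing in the documents establishes it.

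Finally, the analysis is secondary and exploratory, and the device may not display a peak. Both are accepted; the fix does not depend on a peak display.

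**Conclusion.** The point holds in a limited form. The plan names an event but gives no rule for detecting or deriving it. On the natural reading of a 15-minute entry, any excursion shorter than 15 minutes can be missed, and the count can only be too low. How low cannot be fixed from the documents: under the assumptions above, capture of a single excursion runs from 7% at 1 minute to 100% at 15 minutes or more. The consequence is lost events and precision in one secondary chi-square, and a low event rate carried into the full trial. Plasma hemoglobin, procedure time and adverse events do not use the threshold. The change is worth making before data collection because it is cheap and the missing values may be unrecoverable.

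**What to change.** On the Data Collection Form:
- Record any return pressure above 400 mm Hg seen between rows, or the peak for the interval if the device or medical-record log supplies it.
- At each alarm, record the time, the type and the return pressure.
- Keep the 15-minute value as a descriptive measure, and state that it is the reading at that moment.

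In the Statistical Analysis Plan, define the event as any recorded return pressure above 400 mm Hg during the encounter, and name the data source. If the medical record is to be used, state how often it logs pressure.

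The cost is a revised form, a sentence each in Study procedure and the Statistical Analysis Plan, and a few extra entries in encounters with alarms. The nurse is already at the bedside with the form. No clinical rule changes.
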